## 5.2. Encouragement design

Even if random sample of potential participants (surveyed persons) is representative, the decision about the participation in the study may bias its results, as it is made (or rejected) by a potential participant. The assumption of ideal participation of all surveyed persons in the testing is unrealistic. The next step would be to assume self-selection based on the observed characteristics of the surveyed. But it is doubtful that during a telephonic interview all observed individual characteristics which may affect the decision about the participation may be identified and quantified. For this reason, the final assessment of the prevalence will be biased. To surpass the issue of non-observable decision about the voluntary participation, the encouragement design will be used in this study.

A randomly selected subgroup of the surveyed will be offered a benefit related to the study participation, free-of-charge taxi to the place of testing. This offer will be made during the interview. Such randomization will permit to assess the proportion of infected in the group of people whose decision to participate in the testing changes depending to this benefit. The prevalence assessed in this manner has higher external validity than the prevalence in the group of people who make the decision without external encouragement.

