### **3.4. Ethical and legal aspects**

Currently, results of the studies of SARS-CoV-2 infection prevalence in the population have key importance for public health in particular regions as well as at national and international levels. Conduction of such observational population studies is a key objective of scientific and practical medical institutions to be able to inform the society about the current epidemiological situation.

This observational study will involve blood sampling for the antibodies test; this procedure has minimal risks for the health. Participation in the study will not affect medical decisions

in any manner. The nature of participation is completely voluntary. The participants will be informed about the results, but it is not recommended to interpret these results from the point of view of protection from the infection.

This study will be conducted in adherence to applicable local, regional, and national laws and regulations. Non-interventional epidemiological observational studies without investigational drugs are not directly regulated by International Council on Harmonization (ICH) Good Clinical Practice (GCP), but before the start of the study, an ethics committee will perform a review, and the GCP principles will be applied as needed.

This study is being conducted at the territory of the Russian Federation, in accordance to the laws and regulations applicable to epidemiological observational studies. No personal data will be used in data analysis or transferred to the European University at St. Petersburg as well as to laboratories performing the tests.

Participation in the study is completely voluntary and is possible only after the familiarization with the Information Sheet (Appendix 3), study details explanation, and signing correspondent Informed Consent Forms (Appendix 3). The participants can withdraw their consent verbally or in written form at any moment. Withdrawal of consent applies to personal information and results of all tests and procedures which would follow the moment of withdrawal, as well as other personal data. Withdrawal of consent does not apply to already collected and analyzed, anonymized and aggregated data, as such data cannot be identified.

Results of this study cannot be the only reason for making decisions about the epidemics control measures, but they can be used in discussion of such measures.

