#### **4. Laboratory diagnostics**

To measure IgG antibodies titer, Abbott Architect SARS-CoV-2 IgG (<https://www.fda.gov/media/137383/download>) assay will be used. According to the manufacturer, the sensitivity of the assay is 100%, and the specificity is 99.6%. With a scientific objective, Coronapass Total Ig assay (Genetico) will also be used, with the sensitivity of 96% and specificity of 100%, according to the manufacturer. Other point-of-care tests can be used to immediately inform participant but not for the research analysis.

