#### **5. Statistical analysis**

##### **5.1. Sample**

In this study, a population of a region with the size of  $N$  is being looked at. Assuming that the number of infected ( $K$ ) in the population is distributed binomially and the serological test is ideal, 2-sided 95% Wilson confidence interval for the prevalence ( $p$ ) is:

$p' \pm z_{0,025} \sqrt{\frac{p'(1-p')}{n+4}}$ , where  $p' \equiv \frac{k+2}{n+4}$ , and  $z_{0,025}$  is the critical level of the standard normal distribution. In this case the sample size  $n$ , needed for the sample error to not exceed  $M$ , with a conservative assumption of hypothetical prevalence of 50%, is:  $n > \left(\frac{1,96 \times 0,5}{M}\right)^2 - 4$ . For the sample error to reach 2%, at least 2397 observations are needed.

If we assume that hypothetical prevalence is 10%, the sample size is less than 900 for the sample error of 2%. Taking into account possible attrition at the repetitive tests, it is planned to enroll at least 1000 participants.

During the study, it is planned to test at least 1000 participants with a highly sensitive (Se) and highly specific (Sp) test, to reach the sample error level of 2%. The calculations above are applicable to a cross-sectional study. In a cohort study, there is a problem of the sample attrition. We assume loss of 5% of participants at the repetitive blood sampling. If 1000 participants provide samples at the first visit, there will be 630 tested participants at Week 36.

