### 5.3.1. Primary objective

**Cross-sectional study:** the main objective of this study is to calculate the proportion of participants with the presence of antibodies (taking into account the threshold recommended by manufacturer) in the total number of tested. Crude value will be equal to the proportion of positive-tested persons in the total number of enrolled. Additionally, standardized values and values in age or gender groups will be calculated as well as an adjusted value based on the total population in a region.

**Cohort study:** the main objective of the cohort study is to compare correspondent values of prevalence in different points in time. This comparison will be made using simple tests and models depending on the type of value (rough, standardized, adjusted).

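### Between-round prevalence comparisons can shift with who returns, because return follows disclosure of the result and no stated correction is tied to return or to the earlier result

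*Protocol*

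**What the plan says.** Protocol Section 5.2 identifies self-selection at one step, the move from being surveyed to being tested: "The assumption of ideal participation of all surveyed persons in the testing is unrealistic". Its remedy is a randomised taxi offer: "A randomly selected subgroup of the surveyed will be offered a benefit related to the study participation, free-of-charge taxi to the place of testing". On timing it says "This offer will be made during the interview". It describes no second randomisation at a later visit.

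Section 3.1 plans up to 10 visits at 4-week intervals and makes the follow-up questionnaires conditional on the participant agreeing to repeat testing. Results are disclosed along the way. Section 3.4 states "The participants will be informed about the results", and Section 4 adds "Other point-of-care tests can be used to immediately inform participant but not for the research analysis".

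Section 5.1 acknowledges attrition as a problem in a cohort but quantifies it only as a loss of numbers: "We assume loss of 5% of participants at the repetitive blood sampling". This takes 1000 participants to 630 at Week 36.

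Section 5.3 lists an uncorrected prevalence, a single imputation for people not tested, a Heckman correction on observed characteristics and a correction on unobserved characteristics. It does not say which round each applies to. On the comparison over time, which Section 5.3.1 calls the main objective of the cohort study, it says: "This comparison will be made using simple tests and models depending on the type of value (rough, standardized, adjusted".

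**The concern.** There are two selection steps, and the protocol's reasoning covers the first. The second, coming back, is taken by people who already know their result. The telephone script in Appendix 1 offers the test partly as a chance to learn whether one has already been infected. A known result could plausibly change the wish to return, in either direction.

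If return does depend on the previous result, the mix of positives and negatives among those tested changes from round to round even when nobody is newly infected and nobody loses antibodies. A simple comparison of rounds would read that change as epidemic dynamics. The confidence intervals would not show it, because they describe sampling error in whoever attended. The taxi offer does not solve this by itself: a single randomisation before the first test cannot separately identify selection into that test and later return that depends on its result. The variable most directly relevant, the person's own earlier result, is on record for every enrolled participant who later drops out.

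**Working it through.** **Inputs from the protocol.** 1000 tested at the first visit, 5% loss at each of nine further visits and 630 at Week 36 (Sections 3.1 and 5.1); planning prevalence 10% and target error 2% (Section 5.1); 95% intervals (Section 5.3).

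**Input not in the protocol.** Return rates by serostatus. These are assumed and varied below.

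**The plan's own figures reproduce.**
- Attrition: 1000 × 0.95^9 = 630.2, against 630 stated. All ten table entries agree to rounding.
- Sample size for a 2% error: (1.96 × 0.5 / 0.02)² − 4 = 2397 at 50% prevalence, as stated; 1.96² × 0.09 / 0.02² − 4 = 860.4 at 10%, consistent with the stated figure of under 900.

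**Sampling margin at 10%, by the Section 5.1 formula.**
- n = 1000: 1.96 × √(0.09 / 1004) = 1.9 points.
- n = 630: 1.96 × √(0.09 / 634) = 2.3 points.

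**Drift.** Hold true status constant, with 100 positives and 900 negatives, no new infection and no seroreversion. Let positives return with probability r₊ per visit. Choose r₋ for negatives so that the Week 36 total stays at the planned 630.2:

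0.1 × r₊^9 + 0.9 × r₋^9 = 0.95^9

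Apparent prevalence at Week 36 is then 100 × r₊^9 / 630.2.

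| Loss per visit, positives (assumed) | Loss per visit, negatives (solved) | Positives still tested at Week 36 | Apparent prevalence at Week 36 | Shift from 10% |
|---|---|---|---|---|
| 3% | 5.24% | 76.0 | 12.1% | +2.1 |
| 4% | 5.12% | 69.3 | 11.0% | +1.0 |
| 5% | 5.00% | 63.0 | 10.0% | 0 |
| 6% | 4.89% | 57.3 | 9.1% | −0.9 |
| 8% | 4.71% | 47.2 | 7.5% | −2.5 |
| 10% | 4.56% | 38.7 | 6.1% | −3.9 |

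The drift builds gradually. With 10% loss in positives, Week 12 has 100 × 0.90³ = 72.9 positives and 900 × 0.9544³ = 782.4 negatives, so apparent prevalence is 72.9 / 855.3 = 8.5%.

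**Would using the earlier result help?** In the 10% row, positives return with cumulative probability 0.387 and negatives with 0.657. Weighting each attender by the inverse gives 38.7 / 0.387 = 100 positives and 591.5 / 0.657 = about 900 negatives, which restores 10%. This works because, in the example, return depends only on the recorded result.

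**The case against.** Several points on the other side stand.

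- **The corrections in Section 5.3 are tied to no round and list no covariates.** A reader might infer that they address only the decision to be tested after the phone call. The text does not say so. The imputation could be read to include missed later visits, and an earlier result could be among the observed characteristics. A statistical analysis plan, not shown here, may settle this. What can be said is that no stated correction is tied to return or to the earlier result, while the comparison method is already stated.
- **The taxi may not be limited to the first visit.** A reader might infer that people brought in by the taxi face later visits without it and leave faster. Neither Section 5.2 nor the scripts in Appendix 1 restrict it to one trip, and no figure supports faster loss in that group.
- **Inclusion criterion 3.2.1.4 requires consent to repeat testing at entry.** Part of the commitment to return therefore sits inside the first decision. Section 3.1 still leaves later agreement to the participant, and the plan itself expects 37% to be gone by Week 36.
- **Section 2.1 describes the cohort's aim as incidence.** Section 5.3.2 excludes those positive at the first test from that rate, so loss of baseline positives does not enter it. The point concerns the prevalence comparison, which Section 5.3.1 nonetheless names as the main one.
- **The size is assumed.** The protocol gives no return rate by serostatus, and the scenarios compound a constant difference over nine visits. Losses of 4% or 6% in positives move prevalence by about 1 point or less. The 3% scenario stays within the 2.3-point margin at n = 630.
- **The 2% target error is calculated for a cross-sectional study.** It is a reference for scale here, not a limit set for the cohort.

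Section 3.1 also allows delayed test data, which softens missed visits but does not make return independent of the result.

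**Conclusion.** The point holds for the comparison of prevalence between rounds. Following the text as written, differences between rounds can reflect who returned as well as infection or antibody loss. With true prevalence constant at 10% and 630 retained, assumed losses in positives from 3% to 10% per visit give an apparent Week 36 prevalence between 12.1% and 6.1%. The larger differentials (8% and 10%) exceed the 2.3-point sampling margin at that visit; the smaller ones do not. Direction and size both rest on return rates that the protocol does not give, so this is a sensitivity range and not an estimate of bias.

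The first-round prevalence is not affected, the exclusion of baseline positives protects incidence from this particular mechanism, and the attrition and sample-size arithmetic is correct. A reader might go further and conclude that the adjusted values at later rounds are certainly biased, or that the taxi instrument fails over time. The protocol does not support either conclusion.

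**What to change.** - State that the taxi-based selection correction applies to the first test.
- For comparisons between rounds within the enrolled cohort, use inverse-probability-of-return weights, or multiple imputation, with a model that includes the previous antibody result, taxi arm, and the phone and clinic covariates. Present this beside the rough and standardized values.
- Report return rates at each visit by previous result and by taxi arm, so that readers can see whether result-dependent return is occurring.

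The first-round correction for unobserved selection should not simply be multiplied into these weights. It yields a model-based prevalence, not a weight for each person, so that product is not defined.

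The cost is analysis wording and some programming; the variables are already collected. Intervals will be somewhat wider. The method assumes that return is independent of current status given the previous result and the covariates. Return that depends on an infection since the last test would not be corrected, and this should be stated as a limitation.

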## 5.3. Data management and analysis

There are several endpoints in this study. All values will be presented with 95% confidence intervals which corresponds to type I error probability of 5%. Depending on the type of variables, correspondent statistical tests and models will be used.

The prevalence will be calculated using the GJRM library for R statistical software. The following parameters will be calculated:

- Uncorrected prevalence;
- Prevalence with a single imputation of results for non-tested participants;
- Prevalence corrected by self-selection of the participants based on observed characteristics (Heckman model);
- Prevalence corrected by self-selection of the participants based on unobserved characteristics;
- Coefficients of regression of the relation between the observed characteristics of the participants and test results.

### 5.3.1. Primary objective

**Cross-sectional study:** the main objective of this study is to calculate the proportion of participants with the presence of antibodies (taking into account the threshold recommended by manufacturer) in the total number of tested. Crude value will be equal to the proportion of positive-tested persons in the total number of enrolled. Additionally, standardized values and values in age or gender groups will be calculated as well as an adjusted value based on the total population in a region.

**Cohort study:** the main objective of the cohort study is to compare correspondent values of prevalence in different points in time. This comparison will be made using simple tests and models depending on the type of value (rough, standardized, adjusted).

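### The crude prevalence is set over those enrolled while the objective is set over those tested; read literally at follow-up, attrition alone would lower the crude value or mask a real rise.

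*Protocol*

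**What the plan says.** Protocol Section 5.3.1, under the cross-sectional study, gives the main objective as the proportion of participants with antibodies "in the total number of tested". The sentence that follows reads: "Crude value will be equal to the proportion of positive-tested persons in the total number of enrolled".

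Under the cohort study, the same section says that "the main objective of the cohort study is to compare correspondent values of prevalence in different points in time", and adds: "This comparison will be made using simple tests and models depending on the type of value (rough, standardized, adjusted". *Rough* is most naturally the crude value defined just above it. The cohort paragraph names no denominator of its own.

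The protocol does not expect the two groups to stay equal. In Section 5.1 "it is planned to enroll at least 1000 participants", and after 5% loss per repeat visit "there will be 630 tested participants at Week 36". The table in Section 3.1 gives the expected count at each of the ten visits. Section 5.3 also lists "Prevalence with a single imputation of results for non-tested participants", so the protocol recognises that some people will have no result. Nowhere is *enrolled* defined.

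**The concern.** Two consecutive sentences give the same primary quantity two denominators. This is not a detail left for a later statistical analysis plan: such a plan could follow either sentence and still claim to comply.

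The choice matters once people stop coming. With a fixed enrolled denominator, a person with no test at a visit adds nothing to the numerator but stays in the denominator, and so is treated as antibody-negative. The crude value then mixes prevalence with the share tested. That share is planned to fall at every visit, so the crude series would drift downwards whatever the virus does. The cohort study exists to track change in prevalence over time, so the artefact falls on its main comparison.

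**Working it through.** **Inputs.** First-visit count 1000 and 5% loss per repeat visit (Section 5.1); expected counts by visit (table, Section 3.1); planning prevalence 10% and target sampling error 2% (Section 5.1).

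**Step 1: reproduce the protocol's figures.**
- Attrition: 1000 × 0.95⁹ = 630.2, stated as 630. All ten counts in the table agree with 1000 × 0.95ᵏ (k = 0 to 9) to within 1.
- Precision at 50%: (1.96 × 0.5 / 0.02)² − 4 = 2397, as stated.
- Precision at 10%: (1.96 / 0.02)² × 0.1 × 0.9 − 4 = 860, consistent with the stated figure of less than 900.

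**Step 2: crude value under each denominator.** Let p be the prevalence among those tested.
- Over tested: (p × tested) / tested = p at every visit.
- Over baseline enrolled: (p × tested) / 1000.

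With p held at 10%:

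| Visit | Tested | Over tested | Over 1000 enrolled |
|---|---|---|---|
| First | 1000 | 10.0% | 10.0% |
| Week 16 | 815 | 10.0% | 8.2% |
| Week 20 | 774 | 10.0% | 7.7% |
| Week 36 | 630 | 10.0% | 6.3% |

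The shortfall at Week 36 is 10.0 − 6.3 = 3.7 percentage points. It first exceeds 2 points, the size of the target sampling error, at Week 20 (10.0 − 7.74 = 2.26; at Week 16 it is 10.0 − 8.15 = 1.85). With p at 20%, the Week 36 value would be 20 × 0.63 = 12.6%.

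**Step 3: the same effect when prevalence rises.** For the enrolled-based value to remain at 10% at Week 36, prevalence among those tested must be 0.10 × 1000 / 630 = 15.9%. A real rise of that size would look like no change.

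**Step 4: could a simple test pick up the artefact?** Take 100/1000 against 63/1000 as independent samples. The pooled proportion is 0.0815, the standard error is √(0.0815 × 0.9185 × 2 / 1000) = 0.01224, and z = 0.037 / 0.01224 = 3.02 (two-sided p = 0.0025). This ignores the correlation between repeated tests on the same person and is only illustrative.

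**Step 5: first visit.** The planning figures treat 1000 enrolled as 1000 tested, which gives no bias. The protocol gives no share of enrolled people without a first result. If that share were 5%, 10% or 20% (assumed values), 10% among those tested would read 9.5%, 9.0% or 8.0%.

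**The case against.** The best defence is that the crude definition sits only under the cross-sectional study, where enrolled and tested are nearly the same people. Consent to the antibody test is an inclusion criterion (3.2.1.3) and inability to perform it is an exclusion criterion (3.2.2.2). Section 5.1 speaks of enrolling 1000, testing 1000, and 1000 giving samples at the first visit as if these were one thing. The untested people in Section 5.3, read with Section 5.2, are most plausibly those surveyed who declined testing. This stands: a reader might infer that the first-visit prevalence is already biased towards zero, and the planning figures do not support that.

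It can also be said that nothing fixes the baseline 1000 as the Week 36 denominator. Section 5.3.2 defines a secondary measure, cumulative seropositivity, on tests at each moment, and *enrolled* may be a translation slip for *tested*. This stands in part. It makes the fixed-baseline reading conditional, but the test-based definition belongs to another measure and nothing in the protocol settles the matter for the crude value.

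A reader might further infer that the cohort will necessarily show a decline, or that every prevalence estimate is affected. Neither follows. If seropositivity rises, the effect is to hide growth and not necessarily to show a fall. The standardised, adjusted, imputed and selection-corrected values are not shown to share the enrolled denominator.

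**Conclusion.** The point holds for the crude value, and mainly at follow-up. Section 5.3.1 is wrong as written: it gives two denominators and carries the rough value into the cohort's main comparison, while the protocol itself plans for the two groups to diverge.

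Under the literal reading, the Week 36 crude value is 0.63 of what it would be among those tested. That factor rests on *enrolled* meaning the fixed baseline count and on the planned 5% loss per visit. The worked series also holds prevalence among those tested constant, and reading the shortfall as bias against the cohort's true prevalence requires drop-out unrelated to serostatus. Data collection, sample size and the randomised taxi offer are untouched, so the error can be put right in the analysis.

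**What to change.** In Section 5.3.1, replace the crude-value sentence so that the crude value at each visit is the number of positives divided by the number of persons with a valid antibody result for that visit. State that delayed tests allowed by Section 3.1 count towards the visit they stand in for. Report the numbers enrolled and untested beside each value.

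Confine the edit to the crude value. Leave the imputed and selection-corrected estimates in Section 5.3 unchanged: they are built to include untested people, and a tested-only denominator there would undo the correction that the encouragement design in Section 5.2 is meant to support.

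The cost is one sentence and two extra reported counts per visit. No new data are needed.
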